9.3.2 Pharmacokinetic Statistical Methodology

The PK parameter estimates for LY3337641 will be compared between formulations and between the fed and fasted states. Log-transformed $AUC(0-\infty)$, $AUC(0-t_{last})$ and C_{max} estimates will be analyzed using a linear mixed-effects model with fixed effects for treatment, period, and sequence and a random effect for subject. The treatment differences will be back-transformed to present the ratios of geometric least squares means and the corresponding 90% CI.

One model will be used for all of the following comparisons:

- Relative bioavailability: test formulation 1 ($T_{1,fasted}$) versus reference formulation (R_{fasted});

- Food effect: test formulation 1 administered in the fed state ($T1_{\text{fed}}$) versus test formulation 1 administered in the fasted state ($T1_{\text{fasted}}$);
- Relative bioavailability: test formulation 2 ($T2_{\text{fasted}}$) versus Test formulation 1 ($T1_{\text{fasted}}$).

Example SAS code:

```
proc mixed data=DATA covtest alpha=0.1;
  class treatment period sequence subject;
  model log_pk = treatment period sequence / ddfm=kr;
  random subject;
  lsmeans treatment / pdiff cl alpha=0.1;
  ods output lsmeans=lsmeans;
  ods output diffs=diffs;
  ods output covparms=cov;
run;
```

The t_{max} will be analyzed non-parametrically. Median of differences and approximate 90% CI for the median of differences will be calculated for the fed versus fasted states and for the comparisons between the different formulations. P-values will also be calculated using the Wilcoxon signed rank test.

9.4 Safety and Tolerability Assessments

9.4.1 Adverse events

Where changes in severity are recorded in the Case Report Form (CRF), each separate severity of the AE will be reported in the listings, only the most severe will be used in the summary tables. A pre-existing condition is defined as an AE that starts before the subject has provided written informed consent and is ongoing at consent. A non-treatment emergent AE is defined as an AE which starts after informed consent but prior to dosing. A treatment-emergent AE is defined as an AE which occurs postdose or which is present prior to dosing and becomes more severe postdose.

All AEs will be listed. Treatment-emergent AEs will be summarized by treatment, severity and relationship to the study drug. The frequency (the number of AEs, the number of subjects experiencing an AE and the percentage of subjects experiencing an AE) of treatment-emergent AEs will be summarized by treatment, Medical Dictionary for Regulatory Activities (MedDRA) version 19.1 system organ class and preferred term. The summary and frequency AE tables will be presented for all causalities and those considered related to the study drug. Any serious AEs will be tabulated.

9.4.2 Concomitant medication

Concomitant medication will be coded using the World Health Organization (WHO) drug dictionary (Version September 2016). Concomitant medication will be listed.

9.4.3 Clinical laboratory parameters

All clinical chemistry and hematology data will be summarized by parameter and treatment, and listed. Urinalysis data will be listed. Additionally clinical chemistry, hematology and urinalysis data outside the reference ranges will be listed.

Values for any clinical chemistry, hematology and urinalysis values outside the reference ranges will be flagged on the individual subject data listings.

9.4.4 Vital signs

Supine vital signs data will be summarized by parameter and treatment together with changes from baseline, where baseline is defined as Day 1 predose (of each period). Figures of mean vital signs and mean changes from baseline will be presented by parameter and treatment.

Furthermore, values for individual subjects will be listed.

9.4.5 Electrocardiogram (ECG)

ECGs will be performed for safety monitoring purposes only and will not be presented.

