9.4.3. Electrocardiograms

For each subject, ECGs should be collected according to the Schedule of Activities (Section 2).

Any clinically significant findings from ECGs that result in a diagnosis and that occur after the subject receives the first dose of the IP, should be reported to Lilly, or its designee, as an AE via eCRF.

For each subject, a single 12-lead digital ECG will be collected according to the Schedule of Activities. Electrocardiograms must be recorded before collecting any blood for safety or pharmacokinetic tests. Subjects must be supine for approximately 5 to 10 minutes before ECG collection and remain supine but awake during ECG collection. Electrocardiograms may be obtained at additional times, when deemed clinically necessary. All ECGs recorded should be stored at the investigational site.

Electrocardiograms will be interpreted by a qualified physician (the investigator or qualified designee) at the site as soon as possible after the time of ECG collection, and ideally while the subject is still present, to determine whether the subject meets entry criteria at the relevant

visit(s) and for immediate subject management, should any clinically relevant findings be identified.

If a clinically significant finding is identified (including, but not limited to, clinically significant changes in QT/QTc interval from baseline) after enrollment, the investigator will determine if the subject can continue in the study. The investigator, or qualified designee, is responsible for determining if any change in subject management is needed, and must document his/her review of the ECG printed at the time of collection. Any new clinically relevant finding should be reported as an adverse event.

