10.3.1.2. Statistical Evaluation of Safety

Safety parameters that will be assessed include clinical laboratory parameters, vital signs, and ECGs. The parameters will be listed and summarized using standard descriptive statistics, as appropriate. Additional analysis will be performed if warranted upon review of the data.

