3. INTRODUCTION

This SAP has been developed after review of the Clinical Study Protocol (final version dated 09 January 2017).

This SAP describes the planned analysis of the safety, tolerability and pharmacokinetic (PK) data from this study. A detailed description of the planned TFLs to be presented in the clinical study report (CSR) is provided in the accompanying TFL shell document.

The intent of this document is to provide guidance for the statistical and PK analyses of data. In general, the analyses are based on information from the protocol, unless they have been modified by agreement between Eli Lilly and Company and CCI. A limited amount of information concerning this study (e.g., objectives, study design) is given to help the reader's interpretation. This SAP must be signed off prior to first subject administration for this study. When the SAP and TFL shells are agreed upon and finalized, they will serve as the template for this study's CSR.

This SAP supersedes the statistical considerations identified in the protocol; where considerations are substantially different, they will be so identified. If additional analyses are required to supplement the planned analyses described in this SAP, they may be performed and will be identified in the CSR. Any substantial deviations from this SAP will be agreed upon between Eli Lilly and Company and CCI and identified in the CSR. Any minor deviations from the TFLs may not be documented in the CSR.

This SAP is written with consideration of the recommendations outlined in the International Conference on Harmonisation (ICH) E9 Guideline entitled Guidance for Industry: Statistical Principles for Clinical Trials¹ and the ICH E3 Guideline entitled Guidance for Industry: Structure and Content of Clinical Study Reports².

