9.4.6 Other assessments

All other safety assessments not detailed in this section will be listed but not summarized or statistically analyzed.

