11. CHANGES FROM THE PROTOCOL SPECIFIED STATISTICAL ANALYSES

There were no changes from the protocol specified statistical analyses.

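### Does the SAP need changing because it presents no ECG data, although the protocol names ECGs for listing and summary?

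*SAP*

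**What the plan says.** Protocol 10.3.1.2 gives the safety parameters as "clinical laboratory parameters, vital signs, and ECGs. The parameters will be listed and summarized using standard descriptive statistics, as appropriate". Protocol 9.4.3 describes how ECGs are used. A qualified physician at the site reads each one promptly, to check eligibility and to manage the subject. On storage it says "All ECGs recorded should be stored at the investigational site". The investigator decides whether a subject continues after a clinically significant finding, which explicitly includes "clinically significant changes in QT/QTc interval from baseline". On reporting it says "Any new clinically relevant finding should be reported as an adverse event".

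SAP 9.4.5 is one sentence: "ECGs will be performed for safety monitoring purposes only and will not be presented". The next subsection, 9.4.6, adds "All other safety assessments not detailed in this section will be listed but not summarized or statistically analyzed". SAP 3 sets the order of precedence: "This SAP supersedes the statistical considerations identified in the protocol; where considerations are substantially different, they will be so identified". SAP 11 then states "There were no changes from the protocol specified statistical analyses".

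**The concern.** The protocol names three groups of safety parameters, and the SAP gives output to two of them. Laboratory data (9.4.3) and vital signs (9.4.4) are listed and summarised, with urinalysis listed only. ECGs get neither a listing nor a summary. The catch-all in 9.4.6 does not bring a listing back, because ECGs have a subsection of their own. Safety assessments that the SAP does not detail therefore receive more output than one the protocol names.

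SAP 11 then denies any change. A reader comparing the study report with the protocol would find a named output missing and no explanation in the section meant to give one. The adverse-event route does not fully replace a summary: a shift in an interval that no physician judged relevant would appear nowhere in the report.

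**Working it through.** No power, error rate or effect estimate is involved. The check is a count of recordings and a comparison of texts.

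**How much ECG data has no output** (Protocol 2, Schedule of Activities)

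- Per period: predose, 1, 2, 24 and 72 h = 5 recordings.
- Per completing subject: 5 × 4 periods = 20, plus 1 at screening and 1 at follow-up = 22.
- For 24 completers: 22 × 24 = 528. If all 32 complete: 22 × 32 = 704.

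These are recordings, not consequences.

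**Whether the difference is one the SAP had to declare**

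- Protocol 10.3.1.2 ends with a qualifier that leaves the sponsor to judge what output is suitable.
- SAP 3 lets the SAP override the protocol's statistical section and requires only substantial differences to be identified.
- The SAP uses the same latitude for urinalysis. It is listed but not summarised (9.4.3), and SAP 11 does not mention that either. The parallel is partial, because urinalysis keeps a listing.
- The ECG decision is not hidden. It has its own heading and gives a reason, which fits the role that protocol 9.4.3 assigns to ECGs.

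**Whether any result changes**

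- The primary endpoint and two of the secondary endpoints are pharmacokinetic ratios (Protocol 4). ECGs do not enter them.
- The tolerability endpoint is the incidence of treatment-emergent adverse events. Clinically relevant ECG findings enter it through protocol 9.4.3, and SAP 9.4.1 lists all adverse events and summarises the treatment-emergent ones by treatment.
- SAP 9.4.7 plans no inferential safety analysis, so an ECG table would be descriptive. All four treatments are active, so it would have no control arm.
- If the adverse events suggested an ECG problem, protocol 10.3.1.2 provides for further analysis after review of the data, and SAP 3 allows supplementary analyses identified in the report.

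**What an ECG table would cost**

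The documents do not say whether ECG values are databased.

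- If they are, the work is one listing and one table. Each parameter has 4 treatments × 5 times = 20 cells, plus 4 × 4 = 16 change cells. The five ECG times all fall within the eight vital-sign times, so that layout could be reused.
- If they are not, values must be transcribed from the site. The documents name only QT and QTc. Adding heart rate, PR and QRS is an assumption.

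| Parameters | Values per subject (20 in-treatment ECGs) | 24 completers | 32 completers |
|---|---|---|---|
| 2 (QT, QTc) | 2 × 20 = 40 | 960 | 1,280 |
| 5 (assumed) | 5 × 20 = 100 | 2,400 | 3,200 |

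**The case for a change.** The strongest case for a change is that the qualifier in protocol 10.3.1.2 most naturally governs the form and extent of output. Giving a named group no output at all goes further than listing urinalysis without a summary. Precedence settles which text governs, but it does not make the statement in SAP 11 accurate. Correcting that statement would take two or three sentences, so cost is no defence for that remedy.

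Part of this stands. SAP 11 would be more accurate with a cross-reference to 9.4.5, and adverse-event reporting captures only findings judged significant or relevant. But the cross-reference would alter no analysis, output or conclusion, and the information is already in the SAP under its own heading.

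A second point is the possible conflict with SAP 9.1, which promises listings of everything databased. It arises only if ECG values are databased. Protocol 9.4.3 keeps the recordings at the site, so they may not be. If they are, the text can be read as ruling out summaries while leaving the general listing rule in force. That reading is open but not certain, since SAP 13.3 uses the idea of presentation for tables, figures and listings together. The detailed outputs are in a separate shell document (SAP 3) that was not available, so it cannot be settled here whether a listing is planned.

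**Conclusion.** The inconsistency is real but minor, and no change to the plan follows. The silence in SAP 11 is a clerical slip: a decision stated and explained in 9.4.5 is not repeated there. The omission itself is a fair trade-off in a pharmacokinetic crossover study where ECGs serve subject management at the site and clinically relevant findings reach the report as adverse events.

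The effect on the pharmacokinetic and treatment-emergent adverse-event results is nil. What is lost is a description of 528 to 704 scheduled recordings, including small shifts that no physician considered relevant. Restoring it would reverse a deliberate choice and could require up to 3,200 transcribed values under the five-parameter assumption.

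This rests on two conditions. Sites must report clinically relevant ECG findings as adverse events, as the protocol requires. And if ECG values turn out to be databased, analysts must follow the listing rule in SAP 9.1. That would be a programming decision under the existing text.

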9.4.6 Other assessments

All other safety assessments not detailed in this section will be listed but not summarized or statistically analyzed.

9.4.7 Safety and Tolerability Statistical Methodology

No inferential statistical analyses are planned.

10. INTERIM ANALYSES

An interim analysis is scheduled to occur after approximately 24 subjects complete the first 3 periods to support an internal formulation decision for clinical planning activities associated with LY3337641. The primary purpose of this interim analysis is to compare the $AUC(0-\infty)$ and C_{max} of $T1_{fasted}$ and R_{fasted} , however all available PK data will be evaluated during the interim. After Period 3, crossover data from approximately 12 subjects for these 2 treatments should be available.

A sample size of 12 subjects will provide a precision of 13% and 20% for the estimate of the geometric mean ratio in AUC and C_{max} , respectively, between the two formulations.

Assumptions are the same as detailed in Section 7.

An additional interim analysis after Period 4 and before the final database lock may be conducted if needed.

11. CHANGES FROM THE PROTOCOL SPECIFIED STATISTICAL ANALYSES

There were no changes from the protocol specified statistical analyses.

13. DATA PRESENTATION

13.1 Derived Parameters

Individual derived parameters (e.g. PK parameters) and appropriate summary statistics will be reported to three significant figures. Observed concentration data, e.g. C_{max} , should be reported as received. Observed time data, e.g. t_{max} , should be reported as received. N and percentage values should be reported as whole numbers. Median values should be treated as an observed parameter and reported to the same number of decimal places as minimum and maximum values.

13.2 Missing Data

Missing data will not be displayed in listings.

13.3 Insufficient Data for Presentation

Some of the TFLs may not have sufficient numbers of subjects or data for presentation. If this occurs, the blank TFL shell will be presented with a message printed in the centre of the table, such as, "No serious adverse events occurred for this study."

Leo Document ID = a3f220ac-34d5-408c-ade8-ef2e7d3d4783

Approver: PPD

Approval Date & Time: 06-Mar-2017 12:24:13 GMT

Signature meaning: Approved

Approver: PPD

Approval Date & Time: 06-Mar-2017 16:06:11 GMT

Signature meaning: Approved

Approver: PPD

Approval Date & Time: 08-Mar-2017 13:12:06 GMT

Signature meaning: Approved

Approver: PPD

Approval Date & Time: 08-Mar-2017 15:07:01 GMT

Signature meaning: Approved
